Inclusion Criteria:	
 
(1) Age 18-65 years;
 
(2) Self-reported use of non-prescribed opioids in past 14 days;
 
(3) Current moderate to severe opioid use disorder by DSM-5;
 
(4) Urine positive for opioids during screening by point-of-care testing (or self-reported illicit opioid use in the past 4 days, confirmed by a trusted source, for remote or other visits in which urine cannot be collected);
 
(5) History of prior opioid overdose within past 3 years;
 
(6) Previously received take-home naloxone;
 
(7) No life-threatening illness likely to progress clinically during trial;
 
(8) Able and willing to provide informed consent, provide adequate locator information, communicate in English, adhere to visit schedule.
 

Exclusion Criteria:	
 
(1) Suicide plan or attempt within 12 months prior to screening;
 
(2) Urine positive only for prescribed agonist maintenance therapy and negative for cocaine and methamphetamine (or self-report of ongoing receipt of agonist maintenance therapy for remote or other visits in which urine cannot be collected);
 
(3) Currently participating in another interventional research study that could possibly impact the study's outcomes of interest;
 
(4) Planning to leave San Francisco/Boston metro area during study;
 
(5) Previously exposed to REBOOT counseling intervention;
 
(6) Any condition that, in the Principal Investigator's judgment, interferes with safe study participation or adherence to study procedures.
 

Study Procedures/ Frequency:	All subjects will complete the following study visits: prescreening, screening, enrollment, study visits every 4 months for a total of 16 months. All study visits, including screening visits, may be done remotely when COVID-19 safety precautions do not permit in-person visits. Follow-up visits may be done remotely when other events restrict a participant from attending in-person visits (e.g. hospitalization, incarceration, inpatient rehabilitation, moving to another part of the country, etc.). Participants may complete a mix of both in-person and remote visits throughout their 16-month participation in the study. A subset of participants will be asked to

---

---

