### **4.3. Exclusion Criteria**

Subjects who meet *any* of the following exclusion criteria are not to be enrolled in this study.

- (1) Suicide plan or attempt within 12 months prior to screening;
- (2) Urine positive only for prescribed agonist maintenance therapy and negative for cocaine and methamphetamine (if urine cannot be collected precautions, this criterion will not apply);
- (3) Currently participating in another interventional research study that could possibly impact the study's outcomes of interest;
- (4) Planning to leave San Francisco/Boston metro area during study;
- (5) Previously exposed to REBOOT counseling intervention;

- (6) Any condition that, in the Principal Investigator's judgment, interferes with safe study participation or adherence to study procedures.

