### 5.1. Subject Enrollment and Treatment Assignment

Active recruitment will occur at a variety of community locations including, but not limited to, syringe access sites, naloxone distribution sites, the Boston Public Health Commission Engagement Center (Boston site only), local community-based organizations, and SUD treatment centers. Additionally, we will utilize passive recruitment methods through distribution of recruitment materials such as posters, cards, and flyers which will be left at places frequented by opioid users. We will also recruit participants via snowball sampling. Any enrolled REBOOT participant (who was consented, screened, and completed the baseline visit) may refer individuals to the study. Participants will be compensated \$40 per person who they refer who is eligible and enrolls in the study (for a total of up to 5 people or \$200). Participants will be informed of the snowball sampling process during study visits.

Individuals who express interest will complete a brief prescreening questionnaire administered by staff either over the phone or in person. Those deemed eligible per the prescreener will then be scheduled for a screening visit where informed consent will be signed, or verbal consent will be given (for remote or other visits in which urine cannot be collected), and final eligibility will be determined. Eligible participants will be scheduled for an enrollment visit at which time they will complete the baseline assessment and be randomized to either the counseling intervention or the attention control group, as described below. Follow-up visits will occur every four months for 16 months and will be completed primarily in person, but may also be completed over the phone if necessary.

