## **8. STATISTICAL CONSIDERATIONS**

### **8.1. Analysis Objectives**

#### **8.1.1. Analysis Objectives**

The primary objectives of this study are:

1. To adapt REBOOT intervention to ensure relevance in a setting heavily affected by fentanyl using the ADAPT-ITT process.
2. To determine if REBOOT, compared to attention control, reduces during 16 months of follow-up
  - a. the number of opioid overdose events, or
  - b. the occurrence of any opioid overdose
3. To determine if REBOOT, compared to attention control increases
  - a. the number of days abstinent from opioid use, or
  - b. days in substance use treatment.

The exploratory objectives of this study are:

- 1) To determine the efficacy of REBOOT first by site, then in affecting several secondary outcomes, such as modifiable risk behaviors and management of witnessed overdose.

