### **8.4. Data Analysis**

#### **8.4.1. Primary Analysis**

- 1) Specific Aim 1: We will utilize ADAPT-ITT to ensure REBOOT's relevance in the context of fentanyl. We will produce a manuscript describing the process and outcomes, similar to that which we produced for a prior adaptation study of Personalized Cognitive Counseling that was accepted as a CDC Evidence-Based Intervention (<https://tinyurl.com/ybx3oqep>). While the manuscript will describe the process and outcomes from each ADAPT-ITT Phase, a major element of this analysis will be the theater test and focus group (Phase 3). Sessions will be audio-recorded and transcribed verbatim. Two independent analysts will develop a codebook and independently code the focus group transcript. The transcript will then be analyzed using standard thematic content analysis. The topical expert review (Phase 6) will also be a key element in

describing the adaptation process, as well as the final product of the adapted intervention manual.

- 2) **Specific Aim 2a:** Number of overdose events occurring during follow-up
  - a. To determine if REBOOT, compared to attention control, reduces the occurrence of any opioid overdose event, we will use generalized estimating equations (GEE) models for the occurrence of any OD event in each reporting period, with robust standard errors to account for within-subject correlation of the repeated measures.
- 3) **Specific Aim 2b:** Occurrence of any opioid overdose event during follow-up
  - a. To determine if REBOOT, compared to attention control, reduces the number of opioid overdose events, we will use GEE Poisson models for the number of OD events in each reporting period, set up in the same way as the model for Aim 2a.
- 4) **Specific Aim 3:** Number of days not using opioids and number of days engaged in treatment for opioid use disorder during follow-up
  - a. To determine if REBOOT, compared to attention control, increases the number of days abstinent from opioid use and days in substance use treatment, we will use GEE Poisson models for each of these outcomes, both set up in the same way as the models for Aims 1 and 2.

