## **Intervention Overview**

## Intervention Overview

### **10.3. Appendix 3. Descriptions and Dates of Amendments**

Amendment: 08/06/2020

1. Adjusted eligibility criterion regarding urine drug screen results. Because of COVID-19 precautions, one site may be in a new space that may not permit checking of urines. This amendment involves a "trusted source verification" protocol in which study staff contact professionals referred by the participant to confirm the participant's recent use of opioids. The process includes a detailed SOP for determining the result of the inquiry.
2. Clarified that eligibility criterion allowing potential participants currently treated with methadone or buprenorphine for opioid use disorder who report illicit opioid use but test negative for illicit opioids on urine drug screen to be enrolled if they test positive for cocaine or methamphetamine does not apply for eligibility assessments that do not include a urine drug screen.
3. Allow verbal consent and redcap consent collection in some situations due to COVID-19 precautions.
4. Added COVID-19 related questions and analyses, as well as remote versus in-person visit analysis plan, include adjustment to compensation for relevant visits.
5. Provide phone with plan in lieu of other compensation for visits when participant does not have personal phone.

Amendment: 12/28/2020

1. Increased screening payment from \$10 to \$20.

Amendment: 08/16/2021

1. Added snowball referrals from participants to recruitment methods. Active study participants will be compensated \$40 for up to five successful referrals to the study.
2. Added to procedures a one-time visit consisting of a brief assessment at the end of study participation. The purpose is to validate study activities in the assessment (specifically the time-line follow-back). Up to 40 participants will be compensated \$50 for this assessment. Consent for this visit will be obtained separately.
3. Specify that we will begin to collect COVID-19 vaccination status during the assessment at follow-up visits.

Amendment: 05/09/2023

1. Updated the number of participants who will be asked to participate in one-time visit consisting of a brief assessment at the end of study participation from 40 to 100.

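### The main model for days in treatment (objective 3b) has no term for treatment at entry, which gives up precision although the information is collected before randomization

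*Combined protocol and SAP*

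**What the plan says.** **Who can enter.** Exclusion 2 in section 4.3 removes people whose screen is "Urine positive only for prescribed agonist maintenance therapy and negative for cocaine and methamphetamine". Someone on methadone or buprenorphine whose urine shows another qualifying drug can enroll. Appendix 3 indicates that this was deliberate: it describes the criterion as "allowing potential participants currently treated with methadone or buprenorphine for opioid use disorder who report illicit opioid use" to enroll if they test positive for cocaine or methamphetamine. Section 5.1 lists among its recruitment sources "local community-based organizations, and SUD treatment centers".

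**A conflict in the same criterion.** Where urine cannot be collected, section 4.3 says "this criterion will not apply". The synopsis instead excludes on "or self-report of ongoing receipt of agonist maintenance therapy for remote or other visits in which urine cannot be collected". The two give different answers for the same person.

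**The outcome.** Section 8.1.1 lists, among the primary objectives, an increase in "days in substance use treatment". Section 8.4.1 words the outcome more narrowly, as "number of days engaged in treatment for opioid use disorder during follow-up".

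**The model.** Section 8.4.1 specifies GEE Poisson models for the two Aim 3 outcomes, "both set up in the same way as the models for Aims 1 and 2". Aim 1 is the qualitative adaptation work and has no such model, so this can only mean the overdose models. The synopsis (Statistical Methods, Specific Aim 2a) describes those: visit as a categorical term and a treatment effect that grows linearly over follow-up. No baseline treatment term is named.

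**Sensitivity analyses.** The same synopsis paragraph plans one that adjusts for prognostic baseline covariates, without naming them. The Aim 2b paragraph repeats the set for overdose counts. The Aim 3 paragraph has no such sentence, and section 8.4.1 lists no sensitivity analyses.

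**What is collected.** Section 5.6.2 includes treatment in the assessment given at enrollment and at every follow-up visit. Section 5.3.1 puts the baseline assessment before randomization.

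**The concern.** Days in treatment over a four-month period should depend heavily on whether a person was already in treatment at enrollment. If the sample mixes people who attend most days with people who attend few or none, much of the spread in the outcome existed before randomization. A model without that information leaves the spread in the error term, so the comparison of arms is noisier than it needs to be.

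There is also a question of interpretation. A person already treated on most days has limited room to gain days, so the pooled ratio averages two effects: bringing people into treatment and keeping them there.

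The plan recognizes the predictor elsewhere. The COVID-19 analyses in section 8.4.2 name treatment status for opioid use disorder among the variables that may affect service use, and say the GEE models there will control for them. The main analysis of treatment days has no matching provision. Planned subgroup and effect-modification analyses cover site, sex and age, but not treatment at entry.

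**Working it through.** **1. The plan's own figure.** The Sample Size section states 80% power for a 59% reduction in any overdose, with 300 participants and 15% loss. Retained per arm: 300 × 0.85 / 2 = 127.5. Control rates, intra-class correlation and significance level are not given, so the figure cannot be reproduced exactly. In a simple comparison of two proportions, p against 0.41p, power is 79.9% at p = 0.21 (two-sided 0.05, assumed); one-sided, 80% is reached at about p = 0.17. Nothing here shows the figure to be wrong, but it concerns overdose. No power is stated for 3b.

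**2. Headroom and the pooled ratio.** A reporting period is 365.25 × (16/12) / 4 = 121.75 days, so the outcome cannot exceed about 122. Let s be the share in treatment at entry, D their mean days per period with no intervention effect, m the mean for the others under control, and R the ratio in those others. Then

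pooled ratio = [sD + (1−s)mR] / [sD + (1−s)m]

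The documents give none of these values. Assume D = 115, m = 20, R = 1.5:

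| s | Control mean | REBOOT mean | Pooled ratio |
|---|---|---|---|
| 10% | 11.5 + 18 = 29.5 | 11.5 + 27 = 38.5 | 1.31 |
| 20% | 23 + 16 = 39 | 23 + 24 = 47 | 1.21 |
| 30% | 34.5 + 14 = 48.5 | 34.5 + 21 = 55.5 | 1.14 |
| 40% | 46 + 12 = 58 | 46 + 18 = 64 | 1.10 |

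Across D of 100 or 115 and m of 10, 20 or 40, the pooled ratio at s = 30% runs from 1.08 to 1.24. This is a consequence of averaging, not of a faulty model.

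**3. Precision.** A simulation used 254 participants, four periods of 122 days, a Poisson log-link model with categorical visit and cluster-robust standard errors (independence working correlation), and 400 runs per setting. Assumed: those in treatment at entry spend 85% of days in treatment with no intervention effect; the others average 20 days per period under control, with a true ratio of 1.75. Days per person were drawn from a U-shaped distribution. Each dataset was analyzed without and with an indicator of treatment at entry.

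| s | Power, unadjusted | Power, adjusted | Gain (points) | Estimated ratio, unadjusted / adjusted |
|---|---|---|---|---|
| 0% | 84.5% | n/a | n/a | 1.73 / n/a |
| 10% | 66.2% | 79.0% | 12.8 | 1.48 / 1.49 |
| 20% | 48.0% | 67.5% | 19.5 | 1.32 / 1.33 |
| 30% | 40.0% | 56.8% | 16.8 | 1.25 / 1.23 |
| 40% | 30.8% | 50.7% | 19.9 | 1.18 / 1.18 |

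With no true effect, both analyses rejected in 3% to 7% of runs at every s.

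The covariate buys precision: at s = 30% the standard deviation of the log ratio falls from 0.135 to 0.096. It does not undo the averaging in step 2, since the estimated ratio is nearly the same with and without it. Neither analysis shows inflated type I error.

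**4. Limits.** Monte Carlo error is about √(0.5 × 0.5 / 400) = 2.5 points for a power near 50%. The simulation uses a constant effect in place of the planned linearly increasing one, and all distributions are assumed.

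**The case against.** The strongest defense is that nothing here is invalid. Randomization balances treatment at entry in expectation, and the pooled ratio is a proper intention-to-treat effect for the population the trial enrolls. That stands in full. Several stronger readings are tempting, and the documents do not support them.

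- **That the plan ignores baseline treatment altogether.** The synopsis sensitivity analysis could include it, and a sponsor could argue that setting up Aim 3 in the same way carries that analysis over. The text does not say so: the extension is written out for overdose counts and not for Aim 3. What remains is a main model without the term and a sensitivity analysis of uncertain reach.
- **That 3b has a proven ceiling.** The documents give neither the share in treatment at entry nor the distribution of days. Section 4.2 requires recent non-prescribed opioid use and current moderate-to-severe disorder, so near-daily treatment throughout follow-up is not assured. Recruitment at a treatment center does not establish agonist status. People in treatment can leave, and preventing that adds days relative to control. Headroom is limited for some participants, not absent.
- **That the estimate is biased, or that 1.5 or 1.75 is the ratio the trial ought to find.** Those values are assumed effects in one subgroup, with zero effect assumed in the other.

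It is also fair to say that treating entry and retention as separate questions is a preference. Splitting the sample costs precision and adds comparisons to an objective with no stated power.

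**Conclusion.** The point holds as a question of efficiency and clarity. Eligibility and recruitment make wide variation in treatment at entry likely, that variation should predict 3b strongly, and the main model does not use it. The cost is precision: about 13 to 20 power points under the assumed inputs, usable for direction and rough size only. A smaller share in treatment, or entry status that persists less, would reduce the gain. No bias is expected, and the pooled ratio remains valid without adjustment.

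Two wording conflicts bear on the point. The synopsis and section 4.3 disagree on exclusion 2 when urine cannot be collected, which affects how many people in treatment enter. The outcome is also named as substance use treatment in one place and as treatment for opioid use disorder in another.

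**What to change.** 1. In section 8.4.1, name days in treatment (or treatment status) from the enrollment assessment as a pre-specified covariate in the main 3b model, defined in the same way as the outcome.
2. State that the sensitivity analyses listed in the synopsis for the any-overdose outcome also apply to Aim 3.
3. Report the 3b effect by treatment status at entry as a supportive, exploratory analysis, noting that each subgroup estimate is less precise than the pooled one. The covariate alone does not separate entry from retention; this analysis describes that difference.
4. Reconcile the synopsis and section 4.3 on exclusion 2 when urine cannot be collected, and use one definition of treatment for 3b.

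Items 1 to 3 need analysis-plan wording only. The assessment already covers treatment before randomization, so no new data collection is required. Fixing the covariate in advance also removes any later choice about it.

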#### **8.4.2. Exploratory Analyses**

Exploratory analyses will estimate the efficacy of REBOOT first by site, then in affecting several secondary outcomes. Some of these include modifiable risk behaviors and management of witnessed overdose. To estimate the effect of REBOOT, compared to attention control, on overdose risk behaviors, as measured by frequency of using opioids concomitant with alcohol or benzodiazepines (the most common modifiable overdose risk behavior), we will use GEE Poisson models with robust standard errors. We will also use GEE Poisson models with robust standard errors to assess evidence that the intervention increases the use of naloxone during overdose events witnessed by participants. We will also conduct descriptive analyses of overdose risk behaviors and events in the prospectively-followed and sizable control population.

**COVID-19 Variables:** Using the adapted REBOOT intake and follow up assessments we will assess whether COVID-19 infection status is associated with an increased risk of opioid overdose. First, we will estimate the proportion of the REBOOT cohort with a history of infection by COVID-19 based on combined TLFB and health record review, then assess trends in this proportion beginning in January 2020. The association of COVID-19 infection with overdose rates will be assessed using the Anderson-Gill extension of the Cox model for repeated failure events, with calendar date as the time scale.

We will also assess the changes during the COVID-19 pandemic in participant OUD treatment and overdose prevention service use (e.g. naloxone rescue kit access at syringe service programs) using GEE repeated measures models for these outcomes in each reporting period. Predictors of primary interest will include indicators for self-report of COVID-19 infection in the current or previous reporting period, the proportion of the current reporting period covered by a local shelter in place order, other COVID-19 public health mandates, and other policy factors. We will also assess trends in self-reported reduced service use due to the public health mandates. Overlap

of participant-specific 4-month reporting periods will be accommodated by including the reported outcomes in the assessment of included calendar month, with robust standard errors accounting for the repeated measures.

**COVID-19 analyses:** Sex, age, gender, race/ethnicity, OUD treatment status, medical and mental health comorbidities, incarceration, and homelessness may affect COVID-19 infection severity and overdose risk. Therefore, we will assess associations of overdose with indicators of any history of COVID-19 infection as well as time since the infection, controlling for these fixed and time-dependent confounders. These variables may also affect OUD service utilization and the impact of shelter in place orders. Therefore the GEE models will control for these fixed and time-dependent confounders. Results will also be analyzed by pre and post-COVID-19 pandemic and remote versus in-person visit status.

**Biological Variables:** Sex and age may affect the efficacy of REBOOT for primary as well as secondary outcomes. We will conduct additional analyses assessing modification of the REBOOT intervention by these factors.

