Participants will then be randomized to receive either the behavioral intervention (n=150) or attention control (n=150). **Randomization** will be 1:1, stratified by site, using permuted blocks of randomly selected sizes. Participants will then undergo the initial counseling visit for the intervention or attention control for the control arm. Attention control will involve watching videos during in-person visits and listening to podcasts during remote visits.

---

The next visit will be scheduled and participants will be compensated for their time.

---

**Months 2, 6, 10, 14:** Participants will be contacted by study staff to update locator form. If contact is successful, participants will be reimbursed \$3 at that time or at their next visit. Staff may attempt more frequent contact with participants at-risk to being lost-to-follow-up, but participants will not be compensated for these additional contacts.

**Follow-Up Visits (Months 4, 8, 12, and 16):** At months 4, 8, and 12, participant will be seen for urine drug screen (in-person visits only), updating of their locator form, assessment (administered by a staff-person blinded to participant's study assignment), followed by counseling for the intervention arm or video or podcast for the control arm.

At month 16, participants will complete activities listed for the monthly visits. Participants in the treatment arm will not receive counseling at month 16 and participants in the control arm will not watch a video nor listen to a podcast, at month 16. Participants will not update their locator form at month 16.

The assessment, which is administered at enrollment and months 4, 8, 12, and 16 includes demographic information (enrollment only); drug use history (enrollment only); extensive opiate overdose questions; drug use, treatment and drug-related risk behaviors; questions about incarceration, severity of dependence, hopelessness, impulsivity, participant satisfaction with the study. The assessment also includes a COVID-19 Impact Assessment with questions about COVID-19 risk, testing, and vaccination history; drug use behaviors; and access to resources during the COVID-19 pandemic.

**Validation Substudy Visit:** Participants may be invited to complete an additional interview after study completion in which they will complete one repeat assessment to assess the validity of the data collection methodology.

---

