## **4. SUBJECT POPULATION**

### **4.1. Number of Subjects and Subject Selection**

At least 300 subjects will be enrolled in this study (150 at each site).

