### Sample Size

**Sample size justification:** We estimate that the proposed sample of 300 participants, randomized 1:1 to REBOOT and attention control, will provide 80% power to detect net 59% reductions in the prevalence of any overdose by the final reporting period in the REBOOT group, conservatively accounting for net loss of 15% of participants by the end of the study. This is considerably smaller than the 83% net reduction observed in the pilot study. In making these calculations, we used data from the pilot to estimate baseline outcome rates by visit in the control condition, as well as the intra-class correlation of the repeated outcomes. Given the extremely high rates of overdose reported in fentanyl-affected areas, our power may exceed current estimates.

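### The exploratory COVID-19/overdose Cox model states no role for site, so its hazard ratio can be biased in either direction if overdose and infection history both differ between the two cities

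*Combined protocol and SAP*

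**What the plan says.** Section 8.4.2 (COVID-19 Variables) specifies, for infection and overdose, the "Anderson-Gill extension of the Cox model for repeated failure events, with calendar date as the time scale". No strata and no site term are stated.

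The next paragraph of 8.4.2 (COVID-19 analyses) defines the exposure by "indicators of any history of COVID-19 infection as well as time since the infection", and names the variables to adjust for: "Sex, age, gender, race/ethnicity, OUD treatment status, medical and mental health comorbidities, incarceration, and homelessness". The overdose association is to be estimated "controlling for these fixed and time-dependent confounders". The service-use GEE models are to control for the same set. Their predictors include "the proportion of the current reporting period covered by a local shelter in place order", together with other mandates and policy factors.

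Site has a role elsewhere. The synopsis has randomisation "stratified by site, using permuted blocks of randomly selected sizes", and the exploratory analyses estimate REBOOT efficacy by site. The additional splits planned for the COVID-19 results are before v after the pandemic and remote v in-person visits. Nothing in the document places site in the COVID-19 models.

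**The concern.** A calendar-date time scale removes only those trends in overdose that both cities share. With a single baseline hazard, an overdose in Boston on a given date is compared with everyone under observation that day, including San Francisco participants. If one city has more overdose and also more (or less) past infection, the contrast between infected and uninfected participants is partly a contrast between cities.

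The by-site estimate of REBOOT efficacy does not help, because it concerns the randomised contrast. Infection is not randomised, so this estimate relies on its adjustment set, and in a two-site study site is an obvious candidate for that set.

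The service-use GEE models raise a related point. Exposure to a local shelter-in-place order depends on city and date. Without a site term, its coefficient can absorb any standing difference between the cities in service use.

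At stake is the interpretation of two exploratory, observational questions: a spurious association could appear, or a real one could be hidden.

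**Working it through.** The plan gives no hazard ratio, event count, infection rate or site-specific overdose rate for this model, so there is no stated figure to reproduce. Two illustrations follow. Both set the true infection hazard ratio to 1, and every rate in them is an assumption. The 150 participants per site (section 4.1) and 16 months of follow-up come from the plan.

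**Closed form.** Let R be the overdose rate ratio, site A to site B, and let pA and pB be the shares of person-time after infection, with equal person-time per site. The unadjusted ratio is

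HR = [(pA·R + pB)/(pA + pB)] ÷ [((1−pA)·R + (1−pB))/((1−pA) + (1−pB))].

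Example with R = 2, pA = 0.30, pB = 0.15: (0.60 + 0.15)/0.45 = 1.667; (1.40 + 0.85)/1.55 = 1.452; ratio 1.148.

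| R | 30% v 15% | 40% v 10% | 10% v 20% |
|---|---|---|---|
| 1.5 | 1.09 | 1.17 | 0.92 |
| 2 | 1.15 | 1.29 | 0.87 |
| 3 | 1.23 | 1.44 | 0.81 |

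With R = 1, or with pA = pB, the result is exactly 1.00. The range 0.81 to 1.44 belongs to these splits and is not a bound: a 10% v 30% split gives 0.88, 0.80 and 0.71 for the three values of R.

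The shares are of person-time, not of people ever infected. If 40% and 10% were the proportions infected by month 16, then under a constant infection hazard from enrolment the person-time share is 1 − p/(−ln(1−p)). That is 1 − 0.40/0.511 = 0.217 and 1 − 0.10/0.105 = 0.051, and the result at R = 2 falls from 1.29 to 1.25.

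**Simulation.** Andersen-Gill fits on calendar time used 150 per site, entry spread over 24 months, 16 months of follow-up, an overdose rate of 0.05 per month at site B, gamma frailty and 25 replicates.

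| R | Monthly infection hazard, A v B | No site term | Site covariate | Site strata |
|---|---|---|---|---|
| 1 | 0.02 v 0.01 | 0.958 | 0.955 | 0.952 |
| 1.5 | 0.02 v 0.01 | 1.010 | 0.942 | 0.942 |
| 2 | 0.02 v 0.01 | 1.082 | 0.967 | 0.966 |
| 2 | 0.03 v 0.01 | 1.187 | 0.975 | 0.976 |
| 2 | 0.01 v 0.03 | 0.805 | 1.011 | 1.009 |
| 2 | 0.015 v 0.015 | 0.931 | 0.933 | 0.933 |

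Monte Carlo standard errors of the mean log HR are 0.025 to 0.041. Levels somewhat below 1 appear in all three columns alike; a longer rerun of the last row with new random seeds gave about 1, so this is simulation noise. The comparison across columns is what matters. Omitting site shifts the log HR by ln(1.187/0.976) = 0.20 in the fourth row and by ln(0.805/1.009) = −0.23 in the fifth. The shift is nil in the first and last rows, where overdose rates or infection hazards are equal.

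**Against sampling noise.** In the fourth row the standard deviation of one trial's log HR is 0.031 × √25 = 0.155, so the shift of 0.20 is a little over one standard error. In the third row it is 0.030 × √25 = 0.15, against a shift of ln(1.082/0.966) = 0.11.

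**The case against.** The strongest case against has five parts.

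- **Silence is not pooling.** The plan says neither pooled nor unstratified, and it does not say that only the named variables will be adjusted for. A reader might infer that the plan commits to one shared baseline hazard and a closed confounder list; the text does not go that far. What stands is that an unqualified Cox model with named confounders, followed as written, has no site term.
- **The consequence is conditional.** A reader might infer that site differences will show up as a COVID-19 effect. That needs both overdose and infection history to differ by city after adjustment. The documents give no infection figures by site, and listed variables such as homelessness and race/ethnicity may absorb part of any difference. The closed form ignores them.
- **The plan does not forecast different overdose rates by site.** The Sample Size remark, "Given the extremely high rates of overdose reported in fentanyl-affected areas", is about power and names neither city. Section 3.1 adapts the intervention for a region affected by synthetic opioids and tests it with a Boston population, which is indirect support and gives no rate.
- **The bias may be small relative to noise.** With infection hazards of 2% v 0.8% per month and a rate ratio of 2, another approximation put the shift in log HR at 0.14 to 0.15, against sampling standard deviations of 0.34, 0.22 and 0.18 at about 140, 360 and 715 events. That holds for those inputs; the larger infection contrasts above exceed one standard error. The bias is comparable to the noise and does not dominate it.
- **The GEE point is not quantified.** The other mandates and policy factors in those models may already capture part of the difference between cities, and a site term would remove some of the policy contrast. Both points are fair.

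**Conclusion.** The omission is real, and its consequence is conditional. As written, the infection/overdose model names no site strata and no site covariate. Its hazard ratio can be biased upward or downward if overdose rates and infection history both differ by city after the listed adjustments. There is no such bias if either is equal.

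Under the assumed rate ratios of 1.5 to 3 and the three tabulated person-time splits, a true hazard ratio of 1 would appear as about 0.81 to 1.44. These are unadjusted illustrations, not estimates for this trial. For the service-use GEE models the argument is qualitative only.

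Priority is minor. The analysis is exploratory and observational, and the randomised REBOOT comparison, the primary objectives and the sample size do not depend on it. It is still worth changing, because the remedy uses a variable that is already a randomisation stratum.

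**What to change.** In section 8.4.2, state that the Andersen-Gill model will have a baseline hazard stratified by site, so that each city has its own calendar-time course of overdose. A site covariate would be the minimum; it removed the bias equally well in the simulation, but it assumes proportional hazards between cities. Add site to the covariates of the COVID-19 service-use GEE models.

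No new data are needed. The cost in the Cox model is some precision, probably little: in the fourth simulated row the Monte Carlo standard error was 0.031 with and without strata. In the GEE models the cost is more substantive. With site included, shelter-in-place and other policy effects would rest mainly on change over time within each city, and the plan should say so when it describes how those coefficients will be interpreted.
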